## **PROJECT SUMMARY**

**BACKGROUND** Screening with cytology has accompanied large decreases in cervical cancer mortality in the US. However, cytology remains a relatively non-specific test resulting in needless invasive procedures for many women. Studies show that young women are specifically vulnerable since over-screening results in overtreatment with excisional therapies that have been associated with premature delivery and emotional distress. Current national guidelines recommend that routine screening be performed at less-frequent intervals and excisional cervical therapies are discouraged in young women. Uptake of these guidelines has been low for several reasons: many women expect annual cytology, physicians may have financial incentives and/or are not aware of current guidelines. **OBJECTIVES** To examine physician- and patient-based interventions designed to decrease overscreening and overtreatment by increasing adherence to US guidelines for women under 30 years of age. Specifically, the interventions will focus on increasing average intervals between screening and decreasing the number of excisional procedures. The long-term objective is to identify effective strategies to increase adherence to screening guidelines nationwide. **METHODS** We will conduct a randomized intervention clinic with two arms and use Family PACT administrative data for sampling, baseline, and outcome assessment. We will select 14 clinics from the Family PACT provider network that evaluate at least 200 female clients under 30 years of age per year. Clinics will be randomized to 1 of 2 arms: 1) mobile application (APP)-based intervention for providers, and 2) APP-based intervention for providers plus patient-centered approach (PCA) intervention. These groups will be compared to a comparison group of 7 clinics chosen at random (those not randomized). The APP intervention is for clinicians' mobile phones and will maneuver them through current guidelines based on age and condition. The PCA intervention will be patients' education using a tablet at the time of check-in to assist in understanding guidelines, asking questions of their providers, and assist them in evaluating treatment options. Family PACT serves predominantly uninsured women and 40% of clients are Latina. Development of the interventions will be conducted with input from all stakeholders including women from the community who are members of the National Cervical Cancer Coalition, and the Latina Contra Cancer, the American Congress of Obstetricians and Gynecologists, the State Office of Family Planning, the American Society for Colposcopy and Cervical Pathology and Quest laboratories. We plan to enroll 7 sites into each intervention arm with an average of 2800 to 3500 women aged 21-29 years per arm with a similar number of sites and women randomly chosen for the comparison arm resulting in a total of 21 sites and 8400-10500 women. Outcomes will be compared between study arms using t-test adjusting for clustering by clinic. **PATIENT OUTCOMES** We will use Family PACT claims data to calculate for each clinic by age, the number of and average interval between cytology specimens, colposcopy examinations and the number of excisional procedures. **SIGNIFICANCE** We will define successful interventions that will reduce unnecessary screening and treatment for cervical cancer screening in young women.

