## **STUDY DESIGN**

### **Overview**

This is a clustered randomized trial with individual clinics serving as the clusters. Clinics from the California Family PACT provider network who serve at least 200 female clients per year <30 years of age will be randomized to one of 2 intervention arms: 1) physician based approach (APP), and 2) APP-based intervention plus patient-centered approach (PCA). We will reach out to eligible sites to identify which sites are willing to participate. Of these, we will randomize 14 clinics to one of the two intervention arms. These groups will be compared to a comparison group (those not randomized). Since Family PACT data is available for all sites, randomization is not necessary for the comparative groups. However, attention to size, cultural make-up and public versus private information will be accounted for in identifying 7 sites for comparison. Seven sites in each arm/group will result in an average of 2800-3500 women per arm/group—total of 8400-10500 women.

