Our goal is to identify 14 provider sites that each serve at least 200 female clients aged 21-29 years that are willing to participate in study and be randomly assigned to one of the two research arms. We will also identify sites with similar inclusion criteria who but are not participating and of these, 7 sites will be randomly selected for comparison so that this comparison arm would result in a similar number of women aged 21-29 years. We will use variables from the following Family PACT administrative databases to determine the sampling universe: Provider enrollment, client enrollment, and claims databases. We excluded Family PACT providers who are Planned Parenthood (PP) affiliates from our sampling universe because they have a unique monitoring and tracking system of cervical cytology testing that assures adherence to guidelines hence, they would not be representative of other primary care settings. We will also exclude those that already have on average long intervals (>30 months) since they likely already adhere to guidelines. To maintain efficiency, we will focus on Southern California sites that serve the greatest number of women. These include Los Angeles, Orange, San Diego, Riverside, Santa Barbara, San Bernardino, Imperial, Kern, Ventura, and Fresno counties. Within these counties, there are 1,114 private sector clinics, 456 public sector clinics serving a total of 1,280,846 clients. The average age of these women is 27.4. Sixty-nine percent identify as Latina, 15% as white, 6% as black, and 7% as Asian/Pacific Islander. Forty-six percent state that Spanish is

there primary language. Sites that send their cytology to Quest laboratories will also be identified to allow for consistent cytology collection medium and processing.

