## **Selection of Participants**

### *Inclusion Criteria*

#### Intervention arms:

We will identify Family PACT providers who meet the following inclusion criteria:

- Is located in one of the ten Southern California study counties
- Clinical care visits occurred to at least 200 women aged 21-29 years in FY 11/12
- Has a calculated average cytology interval of < 30 months (based on last 3 years)
- Cytology is sent to Quest laboratories

For comparison, we will select from the following:

- Is located in one of the ten Southern California study counties
- Clinical care visit occurred to at least 200 women aged 21-29 years in FY 11/12
- Has a calculated average cytology interval of < 30 months (based on last 3 years)
- Cytology is sent to Quest laboratories

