## **Study Implementation Procedures**

### *Study Enrollment Procedures*

#### Contacting sites:

A letter will be sent to all clinic administrators of eligible sites explaining the study. A follow-up phone call will occur one week later. We will explain the study over the phone and those interested and agree to participate will be identified as clinics eligible to randomize to an intervention arm. If more than 14 sites agree to participate, we will let the sites know that they may not be asked to participate. If more than 14 sites agree, the 14 sites will be chosen based on identifying a balance of private and public clinics so that the average number of women aged 21-29 years is 500, and a relative geographic distribution among the 10 counties and that both English and Spanish languages are well represented according to the county's proportion of Hispanics.

Of those eligible for the comparison sites, we will identify sites using the eligibility criteria, and randomly identify 7 sites but with matching for private and public clinics and relative size of

practice which may range from 200 to over 1000 clients. There will be no contact with these sites since the outcomes data will be monitored from the Family PACT claims database.

Randomization:

Block randomization of clinics to one of the two arms will be performed by the biostatistical group at UCLA.

Site set up:

[name] and the PC will visit all 14 identified clinics sites to meet with staff, identify a key contact person for the site, discuss flow issues, and discuss the protocol.

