### *Quality Assurance*

The PC will identify a point of contact for each intervention site with whom to maintain monthly contact via email/telephone, depending on the type of interaction the site staff requests to ensure that the tablet is functional and remind them to use it in clinic flow. We will ask approximately how many times a week the tablet is being used, how many women refused (in the 21-29 year old), how many women were not offered the tablet. We initially will make weekly calls/emails. After the first month, we will make monthly contact.

The PC will visit all participating intervention arm clinics 2-3 times a year. At that time the PC will ensure that the interventions are in place -- tablets are being functional and are being offered to all age-appropriate women attending the clinic, and all provider phones have a functional mobile application. In addition, to collecting satisfaction surveys, the PC will also collect data on any potential factors that may bias or contaminate an arm (i.e., webinars attended by staff on cervical cancer screening, mobile apps present on the other intervention arms, among others.) using the Quality Assurance Survey (See **Appendix M**). This will be collected at the end of the first and second years. Sites will be reimbursed \$1,000 each a year for their participation in the Quality Assurance Project.

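### Nothing stops a comparison clinic from sharing clinicians with a trained clinic; any overlap after baseline would pull the primary contrasts toward no effect, and a check before the comparison draw would prevent it.

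*Combined protocol and SAP*

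**What the plan says.** The Overview under Study Design sets the unit: "This is a clustered randomized trial with individual clinics serving as the clusters". Inclusion Criteria gives the intervention and comparison sites the same four conditions: county ("Is located in one of the ten Southern California study counties"), volume, cytology interval and laboratory. None concerns staff or ownership.

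Four passages govern the choice of comparison sites:
- Project Summary: "These groups will be compared to a comparison group of 7 clinics chosen at random (those not randomized").
- Overview: "attention to size, cultural make-up and public versus private information will be accounted for in identifying 7 sites for comparison".
- Study Population: "7 sites will be randomly selected for comparison so that this comparison arm would result in a similar number of women". The only separation is that the site itself is not a participant.
- Study Enrollment Procedures, Contacting sites: "randomly identify 7 sites but with matching for private and public clinics", plus relative practice size. These sites will not be contacted.

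Choice of Comparators expects some comparison providers to have the app already but takes it that they have had no systematic training. Quality Assurance has the coordinator visit intervention clinics and record "any potential factors that may bias or contaminate an arm". Data Analyses says administrators and physicians at every clinic site will be asked about confounders.

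**The concern.** The APP intervention is an app on the clinician's own phone plus a 30-minute in-person session. Neither is tied to a building. If a trained clinician also sees patients at a comparison site, that site's cytology rate may fall with the intervention. Both primary contrasts use the same seven comparison clinics, so a single leak affects both, toward no difference. The PCA tablet is used in clinic flow and does not travel in this way, so only the APP share of the APP+PCA effect is exposed.

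With seven clinics per group, one fully exposed clinic removes a seventh of the APP contrast. The power calculation assumes no change in control clinics and allows for missing data, but not for dilution.

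**Working it through.** **Inputs** (Sample Size Estimates and Power Calculations): 7 clinics per arm, 430 women per clinic, ICC 0.07, baseline 50%, difference 16% (read as points, 50% to 34%), 1% level (taken as two-sided), 90% power; 297 sites in the comparison pool.

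**1. The plan's own figure.** Design effect = 1 + 429 × 0.07 = 31.03. Clinic-level variances are 0.25 × 31.03/430 = 0.01804 and 0.34 × 0.66 × 31.03/430 = 0.01619. Standard error = √[(0.01804 + 0.01619)/7] = 0.0699. Noncentrality = 0.16/0.0699 = 2.29. Power (t, 12 df) is about 28%; a normal approximation gives about 39%. So 90% does not follow from the stated inputs. It would need an ICC near 0.016 to 0.023, or a change-score analysis with a clinic-level correlation of about 0.83 to 0.88; the plan states neither. That is a separate problem. Below, 90% is taken at face value only to show how dilution acts.

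**2. Dilution.** If c is the average share of the effect reaching the comparison group, the observed difference is 16 × (1 − c). Power of 90% at two-sided 1% with 12 df corresponds to a noncentrality of 4.50, which scales by (1 − c).

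| Scenario (assumed) | c | Difference | Noncentrality | Power |
|---|---|---|---|---|
| No overlap | 0 | 16.0 | 4.50 | 90% |
| One of four equal-volume clinicians shared, at one site | 1/28 | 15.4 | 4.34 | 87% |
| One clinic of seven fully exposed | 1/7 | 13.7 | 3.86 | 77% |
| Two of seven fully exposed | 2/7 | 11.4 | 3.22 | 58% |

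For APP+PCA, if the APP part supplied half of the effect (assumption), one fully exposed clinic gives c = 1/14: 14.9 points and about 84% power.

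**3. Chance of drawing a linked site.** If L of the 297 sites are linked, P(at least one among 7) = 1 − C(297 − L, 7)/C(297, 7). For L = 10, 20 and 30 (assumed) this is 22%, 39% and 53% under a simple random draw. The planned draw is matched, so these are approximate.

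**4. Would it be seen?** Contamination data are collected on visits to intervention clinics. Comparison sites get no contact and no set-up. Data Analyses would have every clinic site asked about confounders, which cannot be done at comparison sites under the no-contact rule. The leave-one-clinic-out analysis covers the control group and could flag an outlying clinic, but would not show why it is outlying.

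**The case against.** The best reply is that no document shows any sharing, so every value of c and L above is assumed. That stands: this is an uncontrolled risk of unknown size, not a demonstrated bias. Several stronger readings are tempting and should not be drawn.

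- **That a leak could never be detected.** Data Analyses plans to ask about extra apps and educational materials, and the jack-knife includes the control clinics. If the enrollment database identifies clinicians, links could also be traced afterwards. Detection is weak, not impossible.
- **That a linked site is a fully trained site.** Training is given in person to providers at the trained practice. A shared owner alone delivers none, and one shared clinician delivers part. The 77% and 58% rows are upper-end cases.
- **That app use in the comparison group is itself the flaw.** The plan accepts it openly, and stable use before baseline largely cancels in a change-from-baseline comparison. Only training or uptake spreading after the start matters.
- **That the Planned Parenthood exclusion proves networks set cytology practice centrally.** The plan says "they have a unique monitoring and tracking system of cervical cytology testing that assures adherence to guidelines" and treats those affiliates as unrepresentative, so they are the exception.
- **That matching on sector and size favours sister sites.** This is conjecture; both factors are broad.
- **That linked sites within an arm seriously understate the standard error.** Two sites with correlation r multiply that arm's variance by 1 + 2r/7: 29% more at r = 1, but 9% at r = 0.3 and 3% at r = 0.1.

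What remains is that the sampling rule permits the overlap, the intervention can move with the clinician, and the plan does not check its assumption that comparison providers are untrained.

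**Conclusion.** The gap holds. The eligibility and selection rules let a comparison site share clinicians, or an owner, with a trained site. Any such overlap after baseline would bias the APP contrast, and the APP part of the APP+PCA contrast, toward no effect. The size cannot be fixed from the documents. For one affected clinic the illustrations run from a loss of 0.6 of 16 points (power about 87%) to 2.3 points (about 77%). They rest on an assumed degree of exposure and on a 90% starting power that the stated inputs do not yield. The direction is conservative for a claim of benefit, but a real effect could be missed. It is worth closing because prevention before the draw is simple, whereas later repair from claims data would be uncertain.

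**What to change.** In Study Population and in Contacting sites:

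1. Draw the 7 comparison sites only after the 14 intervention sites are fixed. Their outcomes come from claims, so a later draw loses no baseline data; make it before any post-intervention data are examined.
2. Before the draw, use the provider enrollment database (if it identifies clinicians or owners) and a question at the set-up visits about where else the providers work. Remove from the 297-site pool any site that shares a clinician with one of the 14, and preferably any under the same parent organisation.
3. For the 14, ask about shared clinicians in the recruitment call. The set-up visit is listed after randomization and would be too late. Randomize sites that share clinicians as one unit, and analyse them so.
4. Reconcile the no-contact rule with the statement in Data Analyses that each clinic site will be asked about confounders.

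The cost is one database check, one question at each stage and a slightly smaller comparison pool, with 297 sites for 7 places. Joining linked sites among the 14 leaves fewer independent units in an arm. The figure of 89 counts eligible sites, not willing ones, so the room to replace a linked site may be smaller than it looks.

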## **STUDY GOAL AND OBJECTIVES**

### **Study Goal:**

This study's goals are to increase physician and patient adherence to cervical cancer screening guidelines with the ultimate aim of obtaining better health and well-being for women under 30 years of age.

### **Study Objectives:**

To examine physician- and patient-based interventions designed to decrease overscreening and overtreatment by increasing adherence to US guidelines for women under 30 years of age. Specifically, the interventions will focus on increasing average intervals between screening and decreasing the number of colposcopy examinations and excisional procedures. The long-term objective is to identify effective strategies to increase adherence to screening guidelines nationwide.

## **BACKGROUND AND SIGNIFICANCE**

### **Impact of Condition on Health of Individuals and Populations**

Beginning in the 1950's routine screening for cervical cancer began in the U.S. using Papanicolaou smear or cytology. Since then, rates of cervical cancer in the U.S. have decreased by more than 60% specifically in women aged 30 years and older. The age distribution of cervical cancer shows that young women (those 30 and younger) rarely develop cervical cancer with rates less than 2 per 100,000. After 30 years of age there is a rise in CC incidence with a median age of 47 years. This observation is closely linked to the natural history of HPV, the cause of cervical cancer. High risk (HR) HPV infections are those types associated with cervical cancer.

HR-HPV is an extremely common sexually transmitted infection that begins shortly after the onset of sexual activity. Partner studies show that HPV is easily transmitted between couples with estimated transmission of 100% after 11 acts of sexual intercourse. Lifetime risk of acquiring a cervical HPV infection is around 80%. HPV is most commonly found in women 25 year and younger with prevalence rates around 20%. Notably, there is a decline in prevalence starting around 30 years of age which is time where CC begins to rise. The high rates observed in young women is closely paralleled by the high rate of low grade abnormalities on cytology in this age group. We now know that these low grade abnormalities are merely benign reflections of active viral replication. We also now know that most (90%) of women will show clearance of these infections which is thought to occur through both innate and adaptive immune responses which likely protect women from re-infections explaining the decline of HPV with age. On the other hand, persistent HPV infection is the cause of cervical cancer and data shows that cervical cancer develops only after years to decades of HPV persistence in the majority of women which explains why young women rarely have cervical cancer and why in a women's 40's her risk increases. Although cytology is used to detect early invasive cancers, it is now used predominantly to detect precancers, which can be easily treated with several modes of therapy. Of note, there has been virtually no change in cancer rates over the last 10 years. This is predominantly due to the limits of cytology. Unfortunately, screening cytology remains relatively insensitive missing approximate 40-50% of significant precancers found on biopsy. Most now refer to the diagnosis of cervical intraepithelial neoplasia (CIN) grade 3 as the only "true" significant precancer and the lower grade CIN 1 as completely benign. CIN 2 diagnosis remains more controversial and discussed later. However, the cytologic categories have used the Bethesda terminology, which uses only two grades: low (L) grade and high (H) grade squamous intra-epithelial lesions (SIL). Recently there has been consensus to use these same terms for histology where CIN 2 and 3 are considered HSIL and CIN 1 is LSIL.

The insensitivity of the cytology to detect CIN 3 led to frequent screening (annually) and the referral of diagnosis that described insignificant disease. The latter occurred because LSIL and HSIL often co-exist. It is not unusual that only cells from LSILs are detected on the cytology smear in women who also have HSIL for reasons not clear but may be that the LSIL cells are shed more easily. Hence current practice guidelines recommend referral of adult women with LSIL as well as HSIL to colposcopy triage where directed biopsies are taken of tissue that appears abnormal. To complicate matters, a more subtle cytologic diagnosis was created referred to as Atypical Squamous Cells of undetermined significance (ASCUS) which were considered not normal but not SIL. The problem remains that the majority of women with

ASCUS or LSIL on cytology have either no disease or LSIL on biopsy and the majority of women with the true HSIL have ASCUS or LSIL on cytology and not HSIL. In a recent meta-analysis, the sensitivity and specificity of detecting CIN 2 or worse was 57 and 97%, respectively if HSIL was used as a cut off—using LSIL, it was 76% and 81%, respectively. The natural history of LSIL shows that over 90% of women with this lesion will have spontaneous regression, hence, treatment of these lesions would be uncalled for in most. HSIL, on the other hand, is considered a true precancer with progression rates to cancer ranging from 5 to 30%. On the other hand, regression rates of HSIL have been reported as high as 70%, specifically in young women. The progression potential of HSIL remains somewhat elusive since HSIL is a mixture of CIN 2 and 3 lesions. Many believe that CIN 2 does not exist and is simply a misdiagnosis of either a lesion that is truly a CIN 1 or a CIN 3. Numerous studies have shown that cytologic and histologic diagnosis are relatively subjective and have poor reproducibility rates between pathologists for all grades of CIN. Very recently, p16 staining, a marker of cell dysregulation induced by HPV, is being used to adjudicate CIN 2 lesions. It is now recommended that lesions diagnosed as CIN 2 by a pathologist be stained for p16 and if negative for p16 staining, the lesion should be downgraded to a CIN 1, or now referred to as LSIL and if positive, categorized as HSIL.

Using ASCUS or LSIL as a cut off results in referring thousands of women who do not need colposcopy and biopsy whereas using HSIL as a cut off results in missing significant disease including cancer. Biopsy is also not without risk in that infection or bleeding, although rare, can occur. Treatments for abnormal biopsy results include ablative (i.e. cryotherapy (freezing), electric dissection, cold coagulation and laser ablation) and excisional (i.e. Loop electrosurgical excision therapy (LEEP), laser conization and cold-knife conization). None of these procedures are without risk. All can be associated with pain, bleeding and infection as well as psychological distress, anxiety and fear. LEEP has become the modality of choice for most practitioners. Cryotherapy has lost appeal since treatment with cryotherapy of large lesions can result in recurrences and excisional therapies allow the margins of the lesions to be evaluated by a pathologist. Although controversial, margins with evidence of disease are more commonly associated with recurrences. There have been a few meta-analysis and systematic reviews examining birth outcomes after CIN treatment. Crane et al in systematic review found that women who had LEEP were more likely to have preterm birth (OR =1.81 95% Confidence Interval (CI) 1.18, 2.76) and low birth weight infants (<2500 g) (OR=1.60, 95% CI 1.01, 2.52; P = .04). No differences were found in C-section, labor induction or neonatal intensive care unit admission. The finding for preterm birth persisted even when controlling for smoking status. In a prospective study, Crane and colleagues reported that LEEP and cold knife procedures were both associated with preterm birth. Two small meta-analysis found that excisional but not ablative treatment was associated with preterm birth. A recent meta-analysis of excisional and ablative therapies by Bruinsma and Quinn found that preterm birth was increased in women who received excisional therapy compared to both a population based (OR=1.97 95% CI 1.78-2.17) and hospital based (OR=2.71 95% CI 1.89-2.49) comparator. Ablative treatment was also associated with increased risk compared to population-based comparators (OR=1.53 95% CI 1.32-1.78) but not Hospital- based. This meta-analysis also compared treatment to women with CIN but no treatment. In this comparison, excisional (OR=1.25 95% CI .98-1.58) had a smaller affect and ablative was not significant (OR = 1.03 95% CI 0.9-1.18).
